3.1. Primary Objective

To assess changes in mental wellbeing

3.2. Secondary Objectives

- To assess in attitudes towards physical activity
- To assess completion and dropout rates

3.3. Hypotheses

- A) Exposure to the intervention will be associated with significantly lower mean score of depression and anxiety by comparison to a waitlist (delayed intervention) control group
- **B)** After the control group is exposed to the intervention, there will be no significant differences in mean depression and anxiety level between the two groups (immediate intervention group, delayed intervention group)
- C) Mean depression and anxiety severity for all participants at the end of the 6-month follow-up period will be significantly lower than baseline severity (prior to intervention), but not significantly different to end-of-treatment severity, indicating maintenance of gains
- **D)** Attitude towards physical exercise will significantly improve following the intervention, and be maintained at the 6-month follow-up period.

4. Study design

This will be a pragmatic, stepped wedge, open-label, randomised controlled trial. Consenting participants will be randomly assigned to two groups, by a research assistant using a computerized randomization algorithm (applying a simple 1:1 randomization schedule). Participants will take part in one of the two 6-week interventions, depending on their group assignment. They will complete an online survey with standardised measures at baseline (prior to starting the interventions), after 6 weeks (after group 1 has finished and prior to group 2 commencing), after 12 weeks (post-treatment) and finally after 6 months (follow-up). All measures will be completed online using an industry-standard survey system which automatically sends email reminders to consenting participants.

The interventions will be delivered using an online approach; weekly online video-conference sessions involving half an hour of psychoeducation and half an hour of physical activity. Both interventions will involve a total of six 1-hour sessions delivered once per week using video-conferencing software that can involve large groups of participants. The study will be carried out in four phases, which are illustrated in Figure 1.

[figure not shown]

Figure 1. Trial design and measurement time-points

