5.3. Secondary analyses

ANCOVA (and sensitivity analyses) described above will be repeated at each of the time-points illustrated in Figure 1 (weeks 0, 6, 12, 36), using the PHQ-A, and using the GAD-A as an outcome, controlling for baseline scores. Outcomes at 6-months follow-up (pooled for both groups) will be compared to outcomes at the baseline assessment, using paired-samples t-tests (or an appropriate non-parametric test depending on the distribution of the data).

These analyses will be repeated at each of the post-intervention time-points illustrated in Figure 1 (weeks 6, 36), using the WEMWBS sub-domain scores. These between and within-group comparisons will also be summarised using effect sizes (Cohen's d).

Post-intervention measures (weeks 6, 36) will be compared to baseline measures (week 0) within each group, using paired-samples t-tests or an appropriate non-parametric test depending on the distribution of the data. Within-sample pre-post treatment effect sizes will also be computed using the method proposed by Minami et al. (2008).

We will carry out an exploratory analysis of knowledge and levels of activity before and after the intervention.

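### Hypothesis B and the maintenance half of hypothesis C take a non-significant test as support for similarity, and section 5.3 omits the end-of-treatment comparison that C needs

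*Protocol*

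**What the plan says.** Protocol section 3.3 states two hypotheses in terms of non-significance.

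- **B**, after the delayed group has had the intervention: "there will be no significant differences in mean depression and anxiety level between the two groups".
- **C**, at 6-month follow-up, has two halves. Mean severity "will be significantly lower than baseline severity (prior to intervention"), which is an ordinary superiority claim. It is also to be "not significantly different to end-of-treatment severity, indicating maintenance of gains".

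The analyses that bear on these are in section 5.3.

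- The ANCOVA is "repeated at each of the time-points illustrated in Figure 1 (weeks 0, 6, 12, 36"), which gives a between-group test at week 12 for B.
- For the pooled sample, "Outcomes at 6-months follow-up (pooled for both groups) will be compared to outcomes at the baseline assessment, using paired-samples t-tests" or a non-parametric alternative.
- "Post-intervention measures (weeks 6, 36) will be compared to baseline measures (week 0) within each group", again by paired test.

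Section 4 places end of treatment at week 6 for group 1 and at week 12 for group 2. Section 5.1 sizes the trial at 67 per group to detect a moderate effect by between-groups ANOVA, with 192 recruited. The protocol gives no equivalence or non-inferiority margin and no interval-based criterion.

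**The concern.** Failing to reject a difference is not evidence that the difference is small. For B, and for the second half of C, the stated result is more likely to be met when the data are less informative, which is the wrong incentive for a claim of similarity. C makes the inference explicit by saying that non-significance indicates maintenance. B only predicts non-significance, but it offers no other criterion by which it could be supported.

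A second problem is separate from the first. The maintenance half of C needs week 36 compared with end of treatment, and no listed analysis does this. The trial could therefore state a conclusion on maintenance that it had not tested, or report a week-12 result as similarity when the interval still allows a material difference between groups.

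**Working it through.** **Is the end-of-treatment contrast planned?**

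| Planned analysis (Protocol) | Compares | Tests week 36 against end of treatment? |
|---|---|---|
| 5.3 ANCOVA, weeks 0, 6, 12, 36 | group 1 with group 2 at one time | No |
| 5.3 pooled paired test | 6-month follow-up with baseline | No |
| 5.3 within-group paired tests | weeks 6 and 36, each with week 0 | No; week 12 is not listed |
| 5.4 change scores | week 0 to weeks 6 and 12 | No |

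**The plan's own figure.** Section 5.1 does not put a number on a moderate effect. Taking d = 0.5, two-sided alpha 0.05 and 80% power, the two-sample t-test needs 63.8, so 64 per group. The stated 67 gives 81.9% power and is slightly conservative. The inflation reproduces: 134 / (1 − 0.30) = 191.4, so 192. The point here does not depend on the gap between 64 and 67. What matters is that the figure serves a superiority test.

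**Hypothesis B at week 12.** In SD units, SE = √(1 − r²) × √(2/n), where r is the correlation with baseline (assumed; the protocol gives none). The 95% half-width is 1.96 × SE. The chance of non-significance comes from the non-central t with non-centrality d / SE. The case of 96 per group is 192 / 2, the whole recruited sample with imputed values counted as observed.

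| n per group | r | SE | 95% half-width | d / SE at d = 0.30 | P(non-significant) |
|---|---|---|---|---|---|
| 67 | 0 | 0.173 | 0.339 | 1.74 | 59.3% |
| 67 | 0.5 | 0.150 | 0.293 | 2.01 | 48.8% |
| 96 | 0 | 0.144 | 0.283 | 2.08 | 45.7% |
| 96 | 0.5 | 0.125 | 0.245 | 2.40 | 33.4% |

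With 67 per group unadjusted, the chance of non-significance is 79% at a true difference of 0.2 SD, 37% at 0.4 SD and 18% at 0.5 SD.

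**Hypothesis C, maintenance half, if the missing contrast were run.** SE = √(2(1 − r)/N), with r the correlation between end of treatment and week 36, assumed to be 0.5 to 0.7.

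| N pairs | r | 95% half-width | 0.15 SD worsening missed | 0.25 SD worsening missed |
|---|---|---|---|---|
| 134 | 0.5 | 0.169 | 59.3% | 18.1% |
| 134 | 0.6 | 0.151 | 51.3% | 10.5% |
| 134 | 0.7 | 0.131 | 39.5% | 4.0% |

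With 192 pairs after imputation, the corresponding ranges are 24 to 46% for 0.15 SD and 1 to 7% for 0.25 SD.

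**What an equivalence criterion would need for B.** With two one-sided 5% tests and a true difference of zero, power = 2Φ(m/SE − 1.645) − 1 for margin m. At m = 0.3 SD, 67 per group and r = 0: 0.3/0.1728 − 1.645 = 0.091, so power is 7%. With r = 0.5 it is 28%. At m = 0.5 SD it is 79% and 91%. For 80% power at 0.3 SD, 191 per group (r = 0) or 143 (r = 0.5) would be needed. The margins are illustrative, because the documents give none.

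**The case against.** Four stronger readings are tempting, and the protocol does not support them.

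- **That poor data make the whole of C easier to confirm.** C also requires a significant fall from baseline, and section 5.3 tests that. Noise makes this half harder to meet, and a complete return to baseline would fail C. The argument applies to B and to the second half of C only.
- **That attrition would produce these results by widening the intervals.** Section 5.2 specifies intention-to-treat with missing data imputed before analysis, so the analysed number may stay near 192. Whether that imputation is sound is a different question. The weakness remains without attrition: at 96 per group, 33 to 46% of true 0.30 SD differences would still be non-significant.
- **That a sizeable relapse would pass as maintenance.** Once the contrast is run on 134 pairs, a worsening of 0.25 SD is missed only 4 to 18% of the time. The exposure is to small losses, around 0.15 SD.
- **That the lack of an untreated control after week 6 is an error.** It is inherent in a waitlist design, and the synopsis already separates the controlled phase from the later ones.

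It can also be said that B only predicts a result, that section 5.3 reports Cohen's d beside the tests, and that a separate analysis plan might add detail. The first is fair, so B should not be described as claiming proof. Effect sizes without intervals or a margin do not repair the inference. The last does not remove the point: section 3.3 itself fixes the criterion, and section 5, which carries the title of a statistical analysis plan, lists paired comparisons that do not match hypothesis C.

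**Conclusion.** The point stands in two parts. First, B and the maintenance half of C use non-significance as support for similarity, with no margin or interval criterion and a sample sized for superiority. For B, a true 0.30 SD difference would go undetected between 33% and 59% of the time, depending on baseline adjustment (correlation 0 or 0.5, assumed) and on whether 67 or 96 per group are analysed. For C, a 0.15 SD worsening would be missed 40 to 59% of the time with 134 pairs (assumed correlation 0.5 to 0.7), while larger losses would usually be found. Second, the comparison that the maintenance half of C depends on is not among the planned analyses, so that half cannot be tested as the plan stands; this part rests on no assumption. Both hypotheses are secondary, and the primary comparison (A) is not affected. The change should be made before analysis.

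**What to change.** 1. Add to section 5.3 the paired contrast of week 36 with each group's own end of treatment (week 6 for group 1, week 12 for group 2), for PHQ-A and for GAD-A, since B and C cover anxiety as well as depression.
2. Reword B and the maintenance half of C as estimates with confidence intervals. Fix a justified margin in advance, in points on each scale. Claim similarity for B only if the 90% interval lies inside the margin. Claim maintenance only if the upper confidence limit for worsening is below it. Otherwise report the result as inconclusive.
3. If no margin can be justified, report both descriptively with intervals and draw no conclusion from non-significance.

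The data are already to be collected, so no visit or participant is added. The cost is the wording, one contrast per scale and the work of justifying margins, for which the protocol offers no SD or important difference. B may well end as inconclusive at this sample size (7 to 28% power at an illustrative 0.3 SD margin with 67 per group), which makes the descriptive option a reasonable choice.

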4.1. Setting and participants

This study will involve adolescents aged 11-18 years old who are on a waiting list for CAMHS services, or have been highlighted by School Champions and School nurses, and are adolescents who would potentially benefit from some low level psychological intervention. The participants will live in the areas covered by RDaSH. Suitable participants should require low level intervention for support in;

understanding their emotions, coping with low mood, anxiety or stress, and learning strategies for improving their overall mental health and wellbeing.

Inclusion criteria

- Any child aged 11-17 (we will accept participants who turn 18 in the trial period) who may benefit.
- Children must attend a school within the Rotherham, Doncaster, North Lincolnshire or Bradford locality

Exclusion criteria

- Adolescents who are already in receipt of psychological therapy
- Adolescents with a diagnosed condition (such as Autism Spectrum Disorder, learning disabilities, severe depression)
- Adolescents experiencing suicidal ideation
- Adolescents with no access to electronic devices
- Anyone who has participated in either Home Goals or Safety Nets before
- Anyone who is 18 at the time of recruiting (we will accept if they turn 18 over the trial period but not before the trial starts)

4.2. Interventions

Home Goals is designed as a low intensity psychoeducational intervention for young people between 11 years and 18 years of age. The sessions combine a physical exercise activity for 30 minutes, led by Scunthorpe United Football Club and Bradford City FC, followed by 30 minutes of psychoeducational information led by CAMHS, the School Nursing service and taken by clinicians trained to provide group therapy.

The programme runs as a one hour session, once a week, for six weeks. The outline of the sessions is as follows:

- Half an hour psychoeducation based on the ACT principles, and looking at why we experience the emotions we do, and how we can control them
- Half an hour light physical activity run by a sports professional

4.3. Measures

Primary outcome measure

The PHQ-A is a nine-item questionnaire; each answered on a 0 to 3 Likert scale. Items cover different aspects of depression and are worded negatively. Item scores are summed to produce a total score (range: 0 to 27), where higher scores indicate greater levels of depression. Psychometric testing has indicated that this measure was valid, reliable and acceptable measure of depression in adolescent respondents (Johnson, Harris, Spitzer & Williams, 2002). Diagnostic, criterion and construct validity were found to be adequate.

Secondary measures

- Participants will be asked to provide some demographic information, including age, gender, ethnicity
- GAD-A
- Questions related to the participants level of activity pre and post-intervention.

4.4. Recruitment, study procedures and data collection

Participant recruitment process

- A promotion and recruitment pack will include: (1) a poster and (2) a promotional video. These promotional materials will be disseminated to CAMHS staff, School Champions, School nurses, local GP surgeries and the sports clubs themselves.
- Patients will be identified from CAMHS waiting lists and will be invited if they meet the inclusion criteria and will be receive treatment via CAMHS for the 12 week duration of the study. Other sites will not identify participants, they will just advertise the trial using the provided materials.
- The team will also organise attendance at relevant NHS/school team meetings conducted remotely (e.g., using MS Teams) to promote the study. The PI may attend one or more of these promotional meetings, but may also delegate attendance to other members of the research team.
- The team will also organise education sessions for parents/guardians who will be consenting for some of the participants, to give them the opportunity to ask questions
- The promotion and recruitment period will last up to four weeks. Promotion activities will commence in March 2021, prior to obtaining ethical approvals. The formal electronic consent process (described below) will be activated once ethical approval is in place. Potential participants will have the opportunity to contact the research team via email to clarify questions, if necessary. The research team will also hold scheduled video-link sessions, which potential participants can attend to ask any questions they may have prior to the deadline for formal consent.
- Promotional materials described above will contain a weblink to an electronic participant information sheet and consent form (when ethical approval has been given). This method will ensure that no paper copies can be lost or misplaced in the post, and will be an efficient way to gather informed consent using an industry-standard and secure online survey system. A sample text for the consent form that will be available electronically is provided in the Appendix. The promotional material will clearly indicate the deadline for application to participate.
- For those participants under 16 a parent/guardian will have to provide consent before the adolescent can participate
- For those participants aged 16-18 they can provide their own consent if they are deemed to have mental capacity. An information sheet will be provided for their parents to ensure they are aware of participation and what is required.
- Consenting participants will be randomly allocated to the online intervention groups, within their regional area. Allocation will be carried out by a researcher who is independent of the research team, using a computerized randomization schedule. Randomisation will be communicated directly to study participants via email within one week of receipt of their electronic consent form.
- The consent and demographic questionnaires will ask for the participants personal email address. This is to ensure we are able to contact the participants throughout the study period (e.g., sending email reminders). Once they have completed the consent form we will email the participants a unique participant pseudonyms, which cannot personally identify any of the study participants. The participant will then use this pseudonym to identify themselves throughout the rest of the study (i.e., to log in to the online session to ensure anonymity is protected when completing the sessions, and as their identifier when they complete the rest of the measures throughout the study). The Grounded Research team will keep a record of the participants email address and associated pseudonym, so if the participant forgets their code they can contact us. The participants email address will then be deleted when the study has completed.
- The measures will be collected by the research team using a secure, web-based, industry-standard data collection system. Therefore, all data collection will be in electronic form, using unique participant pseudonyms, which cannot personally identify any of the study participants. Participants will receive email reminders (sent confidentially by the research team) at the relevant measurement points (see Figure 1) prompting them to access the survey via the Qualtrics.
- Consenting participants will be made aware that this is not a CAMHS referral, and if CAMHS input is required they will need to access the support through the usual route.

Organisation of the online intervention workshops

- Participants will access one of the two interventions described above; using NHS-approved video conferencing software.
- The sessions will be held after school hours.
- We expect that those who agree to take part in the trial complete one session for each of the six consecutive weeks, depending on whether participants are allocated to Group 1 or Group 2.

Data collection and safeguarding procedures

- All participants will be asked to complete the demographic, primary and secondary measures described above at a baseline assessment time-point (week "0" depicted in Figure 1 above). Participants will then be asked to complete a short version of this electronic questionnaire at subsequent measurement time-points depicted in Figure 1.
- The measures will be collected by the research team using a secure, web-based, industry-standard data collection system. Therefore, all data collection will be in electronic form, using unique participant pseudonyms, which cannot personally identify any of the study participants. Participants will receive email reminders (sent confidentially by the research team) at the relevant measurement points (see Figure 1) prompting them to access the survey.
- The final study dataset will be stored in a secure University network drive, only accessible to members of the research team, which is located behind The University of Sheffield Firewall. This will ensure the security and adequate storage of research data, consistent with NHS and academic codes of information governance and data protection.
- All analyses will be carried out at a University site, and data will be held in a restricted-access drive. The study dataset will be held at the University for a minimum of 5 years after the conclusion of the study.

Incentives for participation

- The participants will have the experience of being trained by sports development coaches from local sports clubs when they undertake the physical activity sessions
- The participants will have access to low level psychological interventions without referral into CAMHS, or the associated waiting times
- Participants will be provided with a certificate of achievement if they attend at least four sessions
- Participants will be eligible to be included in two prize draws for Amazon shopping vouchers.
- The first prize draw will take place at the end of the 6-week intervention phase for each group (week 12 in Figure 1). To be eligible for inclusion in this prize draw, participants should have attended at least four intervention sessions and have completed the three online surveys up to that point. The prize will be a £20 Amazon voucher, and there will be one prize per participating site (trial site).
- The second prize draw will take place at the end of the 6-month observational phase (week 36 in Figure 1). To be eligible for inclusion in this prize draw, participants should have attended at least four intervention sessions and have completed all four online surveys. The prize will be a £50 Amazon voucher, and there will be one prize per participating site (trial site).
- In accordance with the University of Sheffield's policy for the ethical use of incentives in research, the prize winners will receive their electronic voucher code via email and they will be asked to return a signed receipt via email, which includes their name and work address, which is essential for auditing purposes and for legal reasons.

5. Statistical analysis plan

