Interventions	A 6-week, psychoeducation and physical education course consisting of online live psychoeducation sessions and physical activity sessions	
Randomization and data collection	Consenting participants will be randomly assigned to two groups; 1 and 2. Participants in both groups will be asked to complete outcome measures at an initial baseline assessment, after which only participants in group 1 will access a 6-week intervention (controlled phase). Next, group 2 will access the intervention during a 6-week period (full implementation phase). Finally, we will collect further outcome measures 6 months after both groups have completed the intervention (follow-up phase).	
Planned Sample Size	Minimum recruitment target of 192 participants, expecting 30% attrition.	
Data analysis method	 Trial data will be summarised using a CONSORT diagram and analyses will be based on intention-to-treat principles. The primary analysis will compare between and within-group differences in PHQ-A at baseline and 6 weeks, using ANOVA. Secondary analyses: between and within-group analyses will be conducted for GAD-7 and the physical activity measure at baseline and 6 weeks using ANOVA. Between-group and within-group effect sizes will be calculated using Cohen's d. Completion / dropout rates will be compared between groups using chi-square analysis. 	
Study Period	18 months (12 months active study period, plus 6 months analyses and dissemination)	

2. Background and rationale

Mental health problems cause huge public health burden in adolescents globally, as evidenced by a 20% prevalence (Belfer, 2008; World Health Organization (WHO), 2005). In the UK, the demand for Child and Adolescent Mental Health Services (CAMHS) services is at an all-time high and recent research shows children and young people referrals have increased by 26% in five years (Crenna-Jennigs & Hutchinson, 2018). Furthermore, 50% of children and young people that are assessed, wait more than 18 weeks to start treatment and over 3% wait over 12 months (Crenna-Jennings & Hutchinson, 2018).

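### The protocol lets participants learn their group before they complete the baseline PHQ-A, which is the covariate of the primary ANCOVA

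*Protocol*

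**What the plan says.** The synopsis (section 1) begins with assignment: "Consenting participants will be randomly assigned to two groups; 1 and 2". Baseline comes next, from people who already belong to a group: "Participants in both groups will be asked to complete outcome measures at an initial baseline assessment".

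Section 4.4 ties disclosure to the consent form: "Randomisation will be communicated directly to study participants via email within one week of receipt of their electronic consent form".

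Section 4 dates the baseline survey only against the start of treatment: "They will complete an online survey with standardised measures at baseline (prior to starting the interventions". The data-collection part of section 4.4 asks everyone for the demographic, "primary and secondary measures described above at a baseline assessment time-point", which it labels week 0. Nothing makes a completed baseline a condition of randomisation or of the allocation email.

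Section 4 describes the trial as open-label, with the measures taken by online survey. Section 5.2 compares mean PHQ-A between groups by ANCOVA controlling for baseline severity, on intention-to-treat principles, with missing data imputed by an expectation-maximization (EM) algorithm.

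The allocator is described in two ways. Section 4 has the assignment done "by a research assistant using a computerized randomization algorithm"; section 4.4 says "Allocation will be carried out by a researcher who is independent of the research team".

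**The concern.** ANCOVA adjustment is safe because a baseline measured before randomisation cannot be affected by the arm. A self-rated score given after the arm is known loses that protection. The comparator here is a delayed start, so the email tells an adolescent who hoped for help either that it begins now or that it begins after a 6-week wait. Either message could change how the PHQ-A is answered, and the adjustment then carries that change into the treatment estimate.

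The same order affects missing data. Someone who disengages on learning their group may leave no PHQ-A at any time-point. EM imputation can keep that person in the analysis, but only on the assumption that absence is explained by what was observed. If it depends on unobserved severity, bias remains.

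An analysis plan cannot repair a baseline that was collected after disclosure. The order of procedures belongs in the protocol.

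**Working it through.** **Order of events.** The claim rests on sequence, and the plan gives no figure to reproduce.

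| Step | Timing given | Where |
|---|---|---|
| Consent | Within a promotion and recruitment period of up to four weeks | 4.4 |
| Random assignment | After consent, listed before baseline | Synopsis |
| Allocation email | At most one week after the consent form | 4.4 |
| Baseline PHQ-A | Week 0, before the interventions | 4 and 4.4 |

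The email and week 0 are never dated against each other. If a participant consents on the first day of a four-week window, is emailed at the one-week limit, and week 0 falls at the end of the window, the group is known for 4 − 1 = 3 weeks before baseline. The interval is longer if the email is sent sooner, and shorter if the consent window is shorter.

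**Effect on the estimate.** With Y the outcome PHQ-A, X the baseline PHQ-A and b the within-arm slope,

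adjusted difference = (Y₁ − Y₂) − b(X₁ − X₂).

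Assume that knowledge of the arm changes only the baseline report, by s SD in one arm. The adjusted difference then moves by b × s in absolute size. With equal SDs at the two time-points, the standardised slope equals the baseline–outcome correlation r. The standard error with the protocol's 67 per group is approximately √((1 − r²) × 2/67). The protocol gives neither b nor s, so both are assumed over a range. The cells show the bias in SD and, in brackets, the two-sided type I error at nominal 0.05 with no true effect.

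| Slope | s = 0.1 | s = 0.2 | s = 0.3 |
|---|---|---|---|
| 0.4 | 0.04 (0.057) | 0.08 (0.080) | 0.12 (0.118) |
| 0.5 | 0.05 (0.063) | 0.10 (0.103) | 0.15 (0.171) |
| 0.6 | 0.06 (0.072) | 0.12 (0.140) | 0.18 (0.256) |
| 0.7 | 0.07 (0.088) | 0.14 (0.206) | 0.21 (0.398) |

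For scale, at slope 0.5 the standard error is √(0.75 × 2/67) = 0.15 SD, so shifts of 0.1 to 0.2 SD give a bias of one-third to two-thirds of a standard error. Section 5.1 gives no number for its moderate effect. If 0.5 SD is assumed, the full range is 0.04/0.5 = 8% to 0.21/0.5 = 42% of it.

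**Direction.** Hypothesis A expects Y₁ − Y₂ to be negative. If disappointment raises the waitlist baseline, or relief lowers the Group 1 baseline, then X₁ − X₂ = −s and the adjusted difference gains +b × s, towards no benefit. Under that mechanism, the excess rejections in the table would mostly favour the control group. If allocation instead leads Group 1 to report more symptoms, or the waitlist fewer, the sign reverses and benefit is exaggerated.

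**The case against.** The strongest reply is that no sentence says participants are told before baseline. One week is an upper limit for the email, week 0 is not dated against it, and Figure 1, which shows the time-points, is not available in the text reviewed. That stands against any claim that every participant will know their group at baseline. It does not remove the point: the synopsis lists assignment first, the email runs from consent, and the plan can be followed to the letter with disclosure before the PHQ-A.

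A reader might also infer that allocation influences who enters the trial. It does not, because consent precedes randomisation and the randomised set is fixed before anyone is told. Only baseline completion and retention are exposed. Nor are early leavers wholly undescribed: section 4.4 refers to consent and demographic questionnaires together, so demographics may already be held. Their severity would not be.

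A lead time of several weeks is also uncertain. The four weeks cover promotion as well as recruitment, and the consent form opens only after ethical approval.

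The sizes are illustrations on assumed inputs, and the top of the type I error range is an extreme case. The most natural mechanism makes the trial conservative. Both points stand, but a bias towards no benefit is still a bias, and its direction is not assured.

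On the allocator, a research assistant could be independent of the research team, so the two descriptions may be compatible. The matter is also separate from the order of baseline. It merits one clarifying sentence.

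**Conclusion.** The point holds as a defect in the order of procedures, with medium confidence. As written, the protocol permits a self-rated, open-label baseline to be collected after the participant knows their arm, and uses it as the covariate of the primary analysis. The bias is slope × shift: about 0.04 to 0.21 SD for assumed slopes of 0.4 to 0.7 and shifts of 0.1 to 0.3 SD, if the outcome itself is unaffected by the baseline reporting shift. It runs towards no benefit under disappointment or relief, and could reverse under other reporting effects. Differential baseline completion and retention add a missing-data problem that EM imputation does not solve if absence depends on unobserved severity. The documents do not support saying that all participants are told before baseline, or that allocation affects who is randomised. The point is worth correcting because the change is cheap and nothing later can substitute for it.

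**What to change.** State one sequence and use it throughout:

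1. Consent, given by a parent or guardian for those under 16.
2. Issue of the pseudonym.
3. Baseline survey (PHQ-A, GAD-A, activity) submitted by the adolescent under that pseudonym.
4. Randomisation.
5. Allocation email, timed from completion of baseline and not from consent.

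The PHQ-A should not simply be attached to the consent form. For under-16s the person consenting is not the person rated, and the pseudonym is issued only after consent.

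Align the synopsis, section 4, and both the recruitment and data-collection parts of section 4.4. In the same edit, say once who generates and releases the allocation, so that sections 4 and 4.4 agree.

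The cost is a reordering of forms that are already electronic. Consenters who do not complete baseline are not randomised, a small downside. The sample size calculation does not change.
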